7. STUDY ASSESSMENT TABLE

Laboratory and clinical parameters during treatment are to be followed using individual institutional guidelines and the best clinical judgment of the responsible physician. **There are no mandatory lab tests required for this study;** if no labs are drawn per physician discretion (based on routine site practice), that is acceptable. It is expected that patients on this study will cared for by physicians experienced in the treatment and supportive care of patients on this trial. Date of registration is Day 1 on study.

TABLE 1. Schedule of Eligibility Screening and Clinical Follow up

	Eligibility Screening	REGISTRATION	Day 1-28	Further event (DCIS or IBC) ⁸	Day 1-180	Every 6M (years 0-5)	Every 12M (years 1-5)	Every 12M (years 6-10) ⁹
Tests & Observations								
History/physical	X					X		X
Weight, height	X							
Pulse, Blood Pressure	X							
Randomization			X					
Biospecimen collection				X				
Blood sample			X	X			X ¹	X ¹
Tissue sample			X	X				
Imaging studies²								
Contralateral MMG							X (both arms)	
Ipsilateral MMG ³	X			X		X (AM arm)	X (surgery arm)	
Bilateral MMG ⁴	X							X (both arms)
Therapeutic procedures					X			
Surgery ⁵					X			
Radiation (optional) ⁶					X			
Discuss endocrine therapy (both arms)					X			
#Adverse Events⁷								
Report AEs (both arms)					X	X	X	

¹ For patients registered after August 14, 2020

² if routine bilateral MMG performed on an annual basis, it can be used for the contralateral MMG findings also (not required if patient has had mastectomy of the indicated breast)

³ ipsilateral mammogram ≤ 120 days of registration (can also include ultrasound or breast MRI)

⁴ bilateral mammogram ≤ 6 months of registration

⁵ for surgery arm only

⁶ for surgery arm only (optional)

⁷ Record any new AE (or increase of a documented pre-existing condition from screening/history) within 30 days (see also section 9.1.1 - Routine Adverse Event Reporting)

⁸ up to four weeks after a further event (DCIS or invasive breast cancer) occurs

⁹ if patient cannot attend in person, status update can be collected over the phone (patient does not have to provide blood draw or submit MMG)

All follow up visits (including imaging) will take place at scheduled month +/- 4 weeks. Time points should be based on day 1 (date of registration); however, if there is an out of window visit, all subsequent visits should use that timepoint as the date of reference.

Table 2: Schedule of PRO surveys

	Baseline	Month 6	Month 12	Month 24	Month 36, 48, 60, 72, 96, 120
Socio-demographics					
ALLIANCE Patient Questionnaire, adapted with employment items ^{94, 95, 96, 97}	X	X - Employment	X - Marital status - Health insurance - Household size/income - Employment	X - Marital status - Health insurance - Household size/income - Employment	X - Marital status - Health insurance - Household size/income - Employment
Medical and Family History					
Family history	X				
Self-Administered Co-Morbidity Questionnaire ⁴⁴	X	X	X	X	X
Genetics			X		
Complementary Therapies					
CAM Measure ⁷⁸		X		X	
Adherence to hormonal therapy					
Medication Adherence measure ^{45,45}		X	X	X	X
Health behaviors/lifestyle factors					
ALLIANCE Patient Questionnaire		X		X	
Smoking ⁸⁴⁻⁸⁷					
Alcohol ⁸⁵⁻⁸⁸					
Physical activity ⁷⁹⁻⁸³					
Diet ⁸⁹⁻⁹²					
Psychological/Emotional					
STAI Trait Y2 ⁵¹	X				
STAI State Y1 ⁵¹	X	X	X	X	X
CES-D-10 ⁷⁵	X	X	X	X	X
Brief COPE ⁷³	X				

Intolerance of uncertainty- Short form ⁷⁰⁻⁷²	X			X	
Quality of life					
SF-36 ⁴³	X	X	X	X	X
EQ-5D-5L ^{78, 79}	X	X	X	X	X
QLACS ⁷⁴	X			X	
Breast-Q (arm, breast side effects, body image, sexuality) ⁴⁸	X	X	X	X	X
Modified BCPT symptom scale (menopausal symptoms) ⁴⁷	X	X	X	X	X
Breast Cancer Pain Questionnaire – Neuropathic symptoms ^{27,49,50}	X	X	X	X	X
Brief Pain Inventory ⁹³	X	X	X	X	X
BC/DCIS knowledge and perceptions					
BCS-DQI ^{54,98}	X			X	
True/False questions ⁵⁵	X			X	
Risk perceptions ⁵⁶	X			X	
Decision-making					
Decisional regret ⁵²			X	X	X
SURE scale ^{76, 77}	X				
Sources of information ⁵³	X				
Costs					
Financial burden (adapted from CanCors, NHIS) ^{57,58}		X			
COMET website questions					
How participant learned about COMET	X	X			
Use of website					

8. ADVERSE EVENTS

8.1. Adverse Events - General Overview

Per the International Conference of Harmonization (ICH) guidelines, an adverse event (AE) is defined as any untoward medical occurrence in a patient or clinical investigation subject administered a pharmaceutical product and which does not necessarily have to have a causal relationship with this treatment. An adverse event can therefore be any unfavorable and unintended sign (including an abnormal laboratory finding, for example), symptom, or disease temporally associated with the use of a medicinal product or protocol-specified procedure, whether or not considered related to the medicinal product or protocol-specified procedure.

8.1.1 Routine Adverse Event Reporting

For the COMET study, patients will receive surgery, radiation therapy, or hormonal therapy. The toxicity profiles of these standard treatments for DCIS have been well described.

Adverse event (AE) data collection and reporting, are done to ensure the safety of patients enrolled in the study. AEs will be reported from study entry until 5 years after registration.

Preexisting conditions will be recorded as part of medical history during Screening. Any new AEs or increase of a documented preexisting condition from screening/history will be recorded from the time of study registration through the end of year 5 on study. AEs are reported in a routine manner at scheduled times according to the study calendar in section 8. All AEs are entered into the eCRFs in Rave.

The following are regarded as expected AEs for the purpose of the study:

- AEs related to image-guided biopsy
- AEs relating to adjuvant treatment for primary breast cancer or recurrence, such as AEs relating to endocrine therapy (examples include tamoxifen, anastrozole)
- AEs relating to radiotherapy such as hematoma, wound infection or seroma
- AEs relating to surgery such as hematoma, wound infection, or seroma.

If an AE occurs that does not meet the criteria above the AE should be reported in RAVE. To report any AEs other than those listed on the *Adverse Events: Solicited form*, answer "Yes, and reportable adverse events occurred" to the question "Were (other) adverse events assessed during this reporting period?" at the bottom of the eCRF. This will roll out the *Adverse Events: Other form* in the same folder in Rave for the reporting of these other AEs.

Some AEs may not be assessed if tests or procedures are not specifically required within the protocol.

AEs should be reported so that they can be monitored and compared between groups, it is unlikely that AEs will be related to active monitoring, due to the minimal nature of this treatment. Therefore, it is expected that AEs will frequently be considered "unrelated to active monitoring". Detection of invasive disease is not an AE, thus this should be recorded elsewhere in the CRF.

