8.1.2 Solicited Adverse Event Reporting

Adverse event data collection and reporting, which are required as part of every clinical study are done to ensure the safety of patients enrolled in the studies as well as those who will enroll in future studies with similar treatments. Adverse events are reported in a routine manner at scheduled times according to the study calendar in Table 1. For this study, the Forms “Adverse Events: Solicited” and “Adverse Events: Other” are used for routine AE reporting in RAVE. AE reporting is only required during years 1-5 of the study (it is not required years 6-10).

Solicited Adverse Events: The following adverse events are considered “expected” and their presence/absence should be solicited and severity graded at each reporting period.

- Allergic Reaction
- Arthralgia
- Fever
- Hot Flashes
- Myalgia
- Acute Coronary Syndrome
- Ischemia Cerebrovascular
- Hypertension
- Nausea
- Fracture
- Osteoporosis
- Cholesterol (High)

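### Section 8.1.1 gives sites conflicting adverse-event instructions, so non-serious procedural complications may be captured inconsistently, mainly in the surgery arm

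*Combined protocol and SAP*

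**What the plan says.** Section 8.1.1 opens broadly. It states: "Any new AEs or increase of a documented preexisting condition from screening/history will be recorded from the time of study registration", continuing to the end of year 5, and then: "All AEs are entered into the eCRFs in Rave".

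It next names four groups of events as expected. Three concern procedures: "AEs related to image-guided biopsy"; "AEs relating to radiotherapy such as hematoma, wound infection or seroma"; and "AEs relating to surgery such as hematoma, wound infection, or seroma". The fourth is adjuvant treatment, with endocrine therapy as the example. The sentence after the list reads: "If an AE occurs that does not meet the criteria above the AE should be reported in RAVE". Sites are then told how to open the Adverse Events: Other form for anything not on the Solicited form.

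The section also gives a purpose for AE reporting: "AEs should be reported so that they can be monitored and compared between groups".

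Section 8.1.2 lists 12 terms, also calls them expected, and says of them that "their presence/absence should be solicited and severity graded at each reporting period".

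**The concern.** A site coordinator reading 8.1.1 meets a general rule to enter everything. A narrower rule follows, tied to a list, and nothing says which prevails. The narrower rule does no work unless listed events are handled differently from unlisted ones, so it invites the reading that they need not be entered.

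The events that depend on this reading are largely the complications of surgery and radiotherapy. Section 1.6 names these among the risks of the surgical pathway, and avoiding them is part of the case for AM. If some sites leave out the non-serious ones, the recorded AE profile makes surgery look safer relative to AM than it was. Section 10.9 sends AE and SAE reports to the DSMB every six months, and Section 11.11 has the DSMB weigh adverse events when it considers whether the trial continues. The effect is therefore not confined to a final table.

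**Working it through.** The plan gives no figure to reproduce here. The check sets the AE instructions side by side.

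**1. Text pointing to full capture**
- The two general sentences of 8.1.1 quoted above.
- Section 7, Table 1, footnote 7, which asks for any new or worsened AE and makes no exception for expected ones.
- The Other-form instruction in 8.1.1. Its test is absence from the Solicited form, not absence from the expected list.
- Section 8.1.2, which names both forms as the routine route.

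**2. Text pointing to an exemption**
- The conditional sentence after the expected list in 8.1.1.
- The form answer that opens the Other form, which requires the site to say that reportable events occurred. This implies that some events are not reportable, and the list just above is the natural place to look for which.

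**3. Does either side settle it?** No. The general sentences come first and the specific one later, with no order of precedence. Footnote 7 refers the reader back, by heading, to the routine-reporting section, which is the one in conflict (it cites the number 9.1.1; the section now stands as 8.1.1).

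**4. Do the solicited terms recapture the listed events?** The 12 terms are allergic reaction, arthralgia, fever, hot flashes, myalgia, acute coronary syndrome, cerebrovascular ischemia, hypertension, nausea, fracture, osteoporosis and high cholesterol. Terms naming a biopsy, surgical or radiotherapy complication: 0 of 12. Fever or nausea could record a symptom after a procedure, but neither identifies the complication.

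**5. What reaches Rave under each reading**

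| Event | On 8.1.1 list | Solicited in 8.1.2 | All AEs entered | Listed AEs exempt |
|---|---|---|---|---|
| Endocrine effect on the solicited form (e.g. hot flashes) | yes | yes | entered | entered |
| Non-serious seroma, hematoma or wound infection after surgery | yes | no | entered | not entered |
| Non-serious radiotherapy complication | yes | no | entered | not entered |
| Non-serious biopsy complication | yes | no | entered | not entered |
| Serious complication of any of these | yes | not needed | entered (8.1.4) | entered (8.1.4) |

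The readings differ in the three middle rows. Section 8.1.4 sets reporting by seriousness, grade and hospitalization, not by expectedness.

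**6. Which arm is affected.** Surgery-arm patients are expected to finish definitive surgery within 60 days of randomization (5.1.2.1), and Table 1 footnotes 5 and 6 mark surgery and radiation as surgery-arm procedures. AM patients have no primary surgery (5.2.2.1). However, they have surgery for invasive progression and may opt for it otherwise (5.2.2.1, 10.7), and biopsies occur in both arms (5.3.2). The imbalance is one of degree.

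**7. Form of the bias.** Let p_S and p_A be the true rates of non-serious procedural complications in the surgery and AM arms, and f the share of those events lost because a site applies the exemption. If f is the same in both arms, the recorded difference is (1 − f)(p_S − p_A). Even identical site behavior in both arms therefore shrinks the absolute difference, and with p_S > p_A this understates surgery-arm harm. At f = 0 nothing is lost; at f = 1 the non-serious procedural difference disappears from the AE data. The documents give none of f, p_S or p_A.

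**The case against.** The strongest reply is that no sentence says listed AEs are left out. The exemption is inferred from a conditional, while several explicit statements favor full capture, and seroma or wound infection has a named route through the Other form. Nor can 'expected' simply mean unreported: endocrine effects are on the 8.1.1 list, yet 8.1.2 calls several such effects expected and requires them to be solicited. AEs are not an endpoint in Section 2.3, and Section 10 specifies no between-arm AE analysis, so the comparison rests on one statement of purpose. The surgical harm stressed in Section 1.2 is persistent pain, which the surveys measure separately (Brief Pain Inventory, Breast Cancer Pain Questionnaire, Breast-Q).

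Much of this stands. A reader might infer that only events outside the list go to Rave, so that surgery-arm harms are omitted from the comparison. The documents do not support that. The word 'only' is absent, the contrary statements are explicit, serious events are reported regardless, and neither biopsy nor surgery is confined to one arm.

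The reply does not remove the conflict. The conditional sentence still has no function if listed events are treated like all others. The opposite use of 'expected' in 8.1.2 adds to the confusion. The surveys begin follow-up at month 6 and record symptoms reported by patients, not clinician-graded complications. The procedure data described in 5.1.2.1 and 6.1.1 do not mention complications.

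**Conclusion.** Section 8.1.1 contradicts itself on whether AEs on its expected list are entered in Rave, and neither 8.1.2 nor footnote 7 resolves it. The exposure is limited to non-serious biopsy, surgical and radiotherapy complications. It falls mainly on the surgery arm, and its direction is towards understating harm there in the comparison that 8.1.1 intends.

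The size cannot be computed. It runs from nil, if every site follows the all-AEs rule, to all non-serious procedural complications, if every site applies the exemption. The direction assumes that such complications are more frequent in the surgery arm and that loss does not fall more heavily on AM. The documents do not show that any event has been lost. The primary endpoint is unaffected, because 8.1.1 records invasive disease outside the AE forms.

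**What to change.** Reconcile 8.1.1, 8.1.2 and Table 1 footnote 7 with one statement: AEs on the 8.1.1 expected list are also entered in Rave, on the Adverse Events: Other form, in both arms. Say what 'expected' means in each section, or use a different word in one of them. Correct the radiotherapy line, whose examples repeat those given for surgery.

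For events already past, either back-enter non-serious procedural complications from site records where feasible, or label the between-arm AE comparison as possibly incomplete for them. The synopsis dates accrual to the end of 2022 and surgery is expected within 60 days of randomization. Most early post-operative events may therefore precede any wording change, so this part should not be skipped.

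The cost is a wording change plus limited site data entry, or a caveat on the AE table. Adding procedural terms to the solicited form, or requiring full back-entry at every site, is a design choice with real site cost; resolving the contradiction does not need it.

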8.1.2 Solicited Adverse Event Reporting

Adverse event data collection and reporting, which are required as part of every clinical study are done to ensure the safety of patients enrolled in the studies as well as those who will enroll in future studies with similar treatments. Adverse events are reported in a routine manner at scheduled times according to the study calendar in Table 1. For this study, the Forms “Adverse Events: Solicited” and “Adverse Events: Other” are used for routine AE reporting in RAVE. AE reporting is only required during years 1-5 of the study (it is not required years 6-10).

Solicited Adverse Events: The following adverse events are considered “expected” and their presence/absence should be solicited and severity graded at each reporting period.

- Allergic Reaction
- Arthralgia
- Fever
- Hot Flashes
- Myalgia
- Acute Coronary Syndrome
- Ischemia Cerebrovascular
- Hypertension
- Nausea
- Fracture
- Osteoporosis
- Cholesterol (High)

8.1.3 Expedited Adverse Event Reporting

Investigators are required by Federal Regulations to report serious adverse events as defined in the table below. Investigators are required to notify the AFT and their Institutional Review Board if a patient has a reportable serious adverse event. The descriptions and grading scales found in the NCI Common Terminology Criteria for Adverse Events (CTCAE) version 4 will be utilized for AE reporting. The CTCAE is identified and located on the CTEP website at: ctep.cancer.gov/protocolDevelopment/electronic_applications/ctc.htm. All appropriate treatment areas should have access to a copy of the CTCAE. SAEs must be entered into Rave as applicable within 24 hours of learning of the event. This will allow the safety monitor to review the information and assess the safety of the patient.

8.1.4 Severe Adverse Event Reporting Requirements

Severe Adverse Events (SAEs) will be reported from study entry until 5 years after registration.

REPORTING REQUIREMENTS FOR SERIOUS ADVERSE EVENTS

NOTE: Investigators **MUST** immediately report to the sponsor (AFT) **ANY** Serious Adverse Events, whether or not they are considered related to the investigational agent(s)/intervention (21 CFR 312.64)

An adverse event is considered serious if it results in **ANY** of the following outcomes:

- 1) Death
- 2) A life-threatening adverse event
- 3) An adverse event that results in inpatient hospitalization or prolongation of existing hospitalization for ≥ 24 hours

4)	A persistent or significant incapacity or substantial disruption of the ability to conduct normal life functions
5)	A congenital anomaly/birth defect.
6)	Important Medical Events (IME) that may not result in death, be life threatening, or require hospitalization may be considered serious when, based upon medical judgment, they may jeopardize the patient or patient and may require medical or surgical intervention to prevent one of the outcomes listed in this definition.
7)	Or is a new cancer (that is not a condition of the study).
8)	Or is associated with an overdose.

ALL SERIOUS adverse events that meet the above criteria **MUST** be immediately reported to AFT via Rave and within the timeframes detailed in the table below.

Hospitalization	Grade 1 Timeframes	Grade 2 Timeframes	Grade 3 Timeframes	Grade 4 & 5 Timeframes
Resulting in Hospitalization > 24h	Enter into Rave within 24h of the sites awareness of the event			
Not resulting in Hospitalization \geq 24h	Not required to enter into Rave	Enter into Rave within 24h of the sites awareness of the event		

9. DATA COLLECTION AND MANAGEMENT

9.1 Data Collection and Submission

Data collection for this study will be conducted through the Medidata Rave electronic data capture (EDC) system, accessible via the AFT website. Access to the trial in Rave is granted through the iMedidata application to all persons with the appropriate roles assigned in AFT CTMS System.

PRO data will be collected predominantly through the PRO Core system hosted at the University of North Carolina (UNC). Staff permissions and access to PRO Core will automatically be granted to any site staff who also have access to the Medidata Rave EDC system. PRO Core data are stored in a secure enterprise-level Oracle database; the databases and web servers are hosted by the UNC Center for Bioinformatics. The approaches for submitting PRO data are described for each survey time-point in Section 7.1.3; the approaches include data entry of baseline paper forms into PRO Core by site staff, mailing follow-up paper surveys directly from patient to DFCI for data entry into PRO Core, and patient completion of the questionnaire online.

9.2 Data Confidentiality

Patient medical information is confidential and may only be disclosed to third parties as permitted by the ICF (or separate authorization for use and disclosure of personal health information) which has been signed by the patient, unless permitted or required by law.

10 STATISTICAL CONSIDERATIONS AND ANALYSIS PLAN

10.1 Overview of the Study Design

The general analytic approach is a prospective randomized trial design where the hypothesis is based upon a non-inferiority endpoint, namely that *2-year invasive breast cancer detection rate is not inferior in the AM group compared to the surgery group* (see **Study Schema**).

10.2 Sample Size, Accrual Time and Study Duration

Power and Sample Size Considerations. Sample size for this study was estimated using a 2-group test of non-inferiority of proportions, with the 2-year invasive breast cancer rate in the surgery group assumed to be 0.10 based on published studies.^{61,62} The non-inferiority margin assumed was 0.05. Based on a 1-sided un-pooled z-test, with alpha=0.05, a sample size of n=446 per group will have 80% power⁶⁴ to detect the specified non-inferiority margin. The proportion of patients who decline the arm to which they are specifically randomized can diminish the estimate of treatment difference, and could also widen the confidence bounds, but the analytical approaches proposed here aim to diminish the impact on bias of the treatment difference. With a 3-year duration of accrual and 2 additional years of follow-up, we anticipate approximately 148 total events.

Analysis of Primary Outcome (See below for outcomes definitions). This trial was designed anticipating non-acceptance of arm allocation, and the proportion of patients that do not accept their arm allocation can lead to bias in estimates of treatment differences. Thus, we plan to complete several analyses of the primary outcome, reporting the primary intent to treat (ITT) analysis as well as sensitivity analyses that are intended to reduce the bias in estimation of treatment difference in this setting.

We assume that a clinically acceptable difference in 2-year invasive cancer diagnosis rate in order to conclude non-inferiority is 5%. Cumulative incidence curves will be used to estimate the invasive cancer diagnosis rates over time, and at the 2-year point, the difference in rates will be estimated and a 1-sided upper confidence bound of (AM-GCC) will be computed, using methods described by Austin.⁶⁵ We will conclude that AM is not inferior to Surgery if the upper confidence bound on the risk difference at 2 years is less than 5%.

ITT Analysis. The ITT analysis of 2-year invasive cancer diagnosis rate will be conducted using all patients, as randomized, and will be completed using Kaplan-Meier estimates, stratified by group, combined with the Greenwood's confidence interval. The difference in invasive cancer risks will be computed from the Cox model with treatment at 2 years, with a 1-sided 95% confidence interval of the difference (AM-GCC) computed.

Sensitivity analyses. Several sensitivity analyses are planned, including a per protocol analysis, as treated analysis, an instrumental variable analysis, as well as a principal stratification analysis.^{68,69} The sensitivity analysis will account for loss of follow-up, rejection of randomization allocation and withdrawals, and pre-randomization factors influencing rejection of randomization, described in further detail below.

Intent-to-treat (ITT) analysis is typically the standard in reporting results of clinical trials. However, in the presence of rejection of randomization allocation (here defined as selecting surgery when randomized to AM, and choosing AM when randomized to surgery), ITT results can be biased;⁶⁶⁻⁶⁸ similarly per protocol (PP) and as-treated (AT) analyses could yield biased estimates, especially since these analyses may no longer maintain balance achieved by randomization. Cuzick et al⁶⁶ outline an approach to measure treatment effect among compliers, which follows the randomization (e.g. ITT), but assures that the estimates are not diluted by allocation changes. Thus, studies using this approach are similarly powered to ITT analysis, but provide appropriately wider confidence limits, which will be critical in a non-inferiority study. Principal stratification approaches can improve upon the width of confidence intervals and can

allow for covariate adjustment to aid in this improvement. Additionally, the covariates can aid in identifying subgroups with differential clinical response or treatment preference.

We recognize the potential to lose patients to follow-up; yet, we consider approaches that could still provide some level of information for all patients who were randomized. Dunn et al⁶⁷ describe instrumental variable methods with inverse probability weighting for missing data and latent class models as two approaches to deal with loss to follow-up. Each approach makes assumptions, most of which are feasible for this trial, but we will report the assumptions as well as the comparative analyses in the literature and disseminate findings. We will also assess sensitivity to departures from these assumptions through simulation studies.

At interim time-points as the study is enrolling, we plan to assess the level of withdrawal from the study completely, as well as the level of rejection of allocation or later changes in treatment (can only occur in Active Monitoring arm). We will utilize these levels to carry out simulation studies, but with parameters based upon ranges around our observations during the trial enrollment in order to assess our ability to maintain unbiased results of the treatment differences, particularly in the context of a non-inferiority setting. We will also implement sensitivity to the assumptions made in these simulations, including missing data mechanism (MD-5). If all of the approaches are generally equal in reducing bias, we will report on the approach that maintains alpha level and appropriate non-inferiority conclusion as our primary focus, but will also report the other approaches as comparators. The simulation results will be reported as evidence supporting conclusions, when applicable.

Participant subgroups and planned subgroup analyses. We hypothesize that both clinical outcomes and PRO measures may be dependent upon treatment arm and patient characteristics. Pre-specified subgroups for assessment of heterogeneity of treatment effect will include (1) **endocrine therapy** (yes/no as well as duration of therapy); (2) **choice of surgery** (lumpectomy or mastectomy); (3) **receipt of radiation** (yes/no); (4) **mode of monitoring** (q 6 month MMG versus additional imaging, i.e. ultrasound or MRI); (5) **race** (African-American women compared to white women; other minorities will also be assessed for HTE, but precision is likely to be low); (6) **menopausal status** (pre-or post-menopausal, as reported by the patient); (7) **baseline risk of invasive breast cancer** based on modified Gail Score; (8) **burden of comorbidities** at diagnosis which will impact the magnitude of clinical benefit derived from surgery for DCIS. These subgroup analyses will be completed using methods described by Austin⁶⁵ to estimate the average treatment effect (ATE) and the average treatment effect for the treated (ATT), using adjusted Cox models. The ATE would answer the question about how outcomes would change if a policy was instituted that all patients eligible for either therapy were only offered the “experimental therapy”, which here is Active Monitoring. We also consider the use of time-dependent methods for endocrine therapy and receipt of radiation therapy, using the Austin approaches as well, with time-dependent covariates in the Cox models.

Definitions of outcomes

Subsequent local breast events (SLBE) events are coded as one of the following types:

- **iINV:** Ipsilateral invasive in-breast cancer (includes chest wall recurrence)
- **iCIS:** Ipsilateral in situ in-breast cancer
- **cINV:** Contralateral invasive in-breast cancer (includes chest wall recurrence)
- **cCIS:** Contralateral in situ in-breast event cancer
- **iLX:** Ipsilateral lymph node cancer
- **cLX:** Contralateral lymph node cancer

Distant breast cancer metastasis (DistMet) is the only non-SLBE breast event considered

Ipsilateral invasive breast event is defined as first occurrence of either of the following:

- (i) *ipsilateral invasive breast cancer*,
- (ii) *ipsilateral lymph node cancer in the absence* of a preceding ipsilateral invasive breast cancer event,
- (iii) *distant breast cancer metastasis if none* of the following events have occurred previously: ipsilateral invasive breast cancer, contralateral invasive breast cancer, ipsilateral lymph node cancer, contralateral lymph node cancer.
- (iv) *breast cancer death if none* of the following events have occurred previously: ipsilateral invasive breast cancer, contralateral invasive breast cancer, ipsilateral lymph node cancer, contralateral lymph node cancer, distant breast cancer metastasis.

Ipsilateral breast event (in situ or invasive) is defined as first occurrence of either of the following:

- (i) *ipsilateral invasive breast cancer* (see definition above)
- (ii) *ipsilateral in situ breast cancer*

Censoring vs Ignoring of events

For all time to event analysis (Kaplan-Meier, Cox models), we have to assign to each occurrence one of the following actions (Table 3):

Time to event outcome	Ipsilateral invasive breast event	Ipsilateral breast event	Disease-specific survival	Overall survival
Ipsilateral invasive in-breast cancer	Event	Event	Ignore	Ignore
Ipsilateral in situ in-breast cancer	Ignore	Event	Ignore	Ignore
Contralateral invasive in-breast cancer	Ignore	Ignore	Ignore	Ignore
Contralateral in situ in-breast event cancer	Ignore	Ignore	Ignore	Ignore
Ipsilateral lymph node cancer	Event if no prior iINV	Event if no prior iINV	Ignore	Ignore
Contralateral lymph node cancer	Ignore	Ignore	Ignore	Ignore
Distant breast cancer metastasis	Event if no prior iINV or cINV or cLX or iLX	Event if no prior iINV or cINV or cLX or iLX	Ignore	Ignore
Death from breast cancer	Event if no prior iINV or cINV or cLX or iLX or DistMet	Event if no prior iINV or cINV or cLX or iLX or DistMet	Event	Event
Death from breast-cancer unrelated cause	Censor	Censor	Censor	Event
Loss to follow-up	Censor	Censor	Censor	Censor

Table 3. See SLBE coding section for abbreviations of iINV, cINV, iLX, cLX and DistMet

Planned subgroup analyses (NCDB Special Study). The large DCIS registry developed through collaboration with the National Cancer Database (NCDB) will allow for the continued collection of long-term outcomes for patients as well as for the comparison of primary and secondary outcomes (when measurable in NCDB) for **AM versus surgery** amongst those patients who are randomized and accept their arm allocation versus those patients who are randomized but do not accept their arm allocation versus patients not registered or randomized to COMET, but who generally meet our broad inclusion criteria for the trial. Patients will be identified from all study sites during the time interval of COMET accrual. These analyses will be from predominantly non-randomized patients, so we plan to utilize observational study approaches for analyses. We will use full regression models (logistic or Cox model, dependent upon outcome measure) to control for potential confounders, including pathology, age, race, academic versus community setting, among others. As in other analyses, we will utilize inverse-probability weighting to handle missing data.⁷⁰

Analyses of long-term outcomes. Analyses of long-term outcomes will follow the approaches outlined above, modifying the year of rate calculations, accordingly. PRO data will utilize longitudinal linear mixed models over time, following appropriate scoring and transformation, if needed.

